# 12.5. Other Efficacy Variables Analyses

## 12.5.1. Parameters related to the primary criterion

The main model (MMRM) will also be used to analyse the endpoints related to the main criterion (individual components of the ocular surface staining score – nasal and temporal interpalpebral and corneal fluorescein staining scores) after 4 weeks of treatment (28 days).

## 12.5.2. Other parameters of efficacy

Corneal fluorescein clearing: the number and percentage of patients reaching a score of 0 at their CFS will be presented by group at each time point (week 2, week 4 and week 12), with the corresponding 95% CI ().

Symptoms of ocular discomfort (individual VAS and their mean) will be analysed with an MMRM model using the corresponding baseline value as covariate, at week 2, week 4 and week 12 for the Schirmer test and TBUT at week 4 and week 12.

Evaluation of the efficacy of the treatment by the investigator will be compared between groups at week 2, week 4 and week 12 by a Wilcoxon test.

An exploratory analysis of the NEI-VFQ (QOL Questionnaire) subscale scores and composite score will also be performed. The change from baseline in either total score or appropriate subscale scores will be summarized using descriptive statistics. At week 4, the mean change from baseline will be compared between the groups using an MMRM model with treatment, visit, and treatment-by-visit interaction as fixed effects, baseline value of the corresponding score and the interaction

between the treatment and the ocular surface staining score at baseline as covariates. In order to give more interpretable results, the corresponding LS means will also be expressed in term of effect-size.

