#### **5.3.2.** Secondary Endpoints

#### **5.3.2.1.** Secondary Efficacy Endpoints

The secondary endpoints are the difference between patients treated with ALOCROSS® and patients treated with VISMED® in:

- The change of OSS score between baseline and D14 and between baseline and D84
- The change of ocular stainings (corneal fluorescein staining (CFS) and clearing and conjunctival staining) between baseline and D28 and between baseline and D84
- The change of symptoms and tear breakup time (TBUT) between baseline and D28 and between baseline and D84
- The change of Schirmer's tear test between baseline and D28 and between baseline and D84
- The overall efficacy evaluation of the investigator after 12 weeks of treatment (84 days)
- The change of subjective assessments evaluation by the patient between baseline and D84

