# 7. SELECTION AND WITHDRAWAL OF PATIENTS

#### 7.1. Patient Inclusion Criteria

Patient eligibility is determined according to the following criteria:

- 1. Male or female patient aged 18 years or above.
- 2. Patient using artificial tears for at least 3 months prior to the Screening visit.
- 3. Patient experiencing at least 2 symptoms of ocular discomfort rated ≥23 mm on the 0 to 100 mm visual analogue scale (VAS) (among itching, eye dryness, sticky feeling, photophobia, pain, burning or stinging, sandy feeling or grittiness, or foreign body sensation) at Screening and Baseline visits.
- 4. OSS score (sum of nasal and temporal interpalpebral conjunctival and corneal vital staining) ≥4 and ≤9 on a modified Oxford scale at Screening and Baseline visits in at least one eye.
- 5. TBUT of  $\leq$ 10 seconds at Screening and Baseline visits and/or Schirmer's tear test of  $\geq$ 3 and  $\leq$ 9 mm/5 min at Screening visit in the same eye that fulfil inclusion criteria #4.
- 6. The patient has signed and dated a written informed consent form prior to the initiation of any study procedures.

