#### Ocular

- 1. CFS score ≥4 on a modified Oxford scale
- 2. Ocular hypertension or glaucoma requiring IOP-lowering medication(s)
- 3. History of ocular trauma, infection or ocular inflammatory condition within the last 3 months before the screening visit.
- 4. Severe blepharitis and/or severe meibomian gland disease
- 5. Filamentary keratitis
- 6. Any ocular surface anomaly not related to DED
- 7. Active ocular infection or history of ocular allergy or ocular herpes
- 8. Patient with only one sighted eye or with a best corrected distance visual acuity  $\leq 1/10$
- 9. Use of any topical ocular treatment other than study device during the study (all non-study topical ocular treatment(s) must be stopped at the screening visit)
- 10. Onset of lid hygiene (whatever the method) less than 2 months before the Screening visit
- 11. Use of topical corticosteroids one month before the Screening Visit

- 12. Use of isotretinoin, ciclosporin, tacrolimus, sirolimus, pimecrolimus or ocular cauterisation procedures 2 months before the screening visit and throughout the study
- 13. Use of VISMED® within 6 weeks prior to the screening visit
- 14. Refractive surgery (e.g. LASIK, LASEK, PRK) within 6 months and/or any other ocular laser/surgery within 3 months prior to the screening visit and during the study
- 15. Insertion of temporary punctal plug(s) within 2 months prior to the Screening visit or permanent occlusion of lacrimal puncta on one or both sides
- 16. Known hypersensitivity to any of the components of the study device or investigational products

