## 10. ASSESSMENT OF EFFICACY

# 10.1. Corneal and Conjunctival Fluorescein Staining

Corneal and conjunctival fluorescein staining will be assessed immediately following the TBUT. Reading will be performed between 1 and 4 minutes after fluorescein instillation for the TBUT, to ensure that the dye does not diffuse into stroma blurring the discrete margin of any staining defects. Both eyes will then be examined at the slit lamp (16X magnification) using a yellow barrier filter and cobalt blue illumination to enhance visibility of staining.

Staining using fluorescein will be graded using the modified Oxford scale (7-point ordinal scale, score 0, 0.5, and 1 to 5 per area [cornea + nasal and temporal conjunctiva]) for cornea and conjunctiva separately, see Appendix A-I Modified Oxford Scale. On this modified scale, the score 0 corresponds to no staining dots and the score 0.5 corresponds to one staining dot per area.

A CFS grade of 0 represents complete corneal clearing.

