# **12.1.2. Study Eye**

The study eye is defined as the eligible eye that fulfils all the criteria listed under the inclusion criteria #4 and #5. If both eyes are eligible, the eye with the highest baseline CFS score will be chosen. If both eyes have the same baseline CFS score, the eye with the lowest Schirmer's test value will be chosen. If both eyes have the same Schirmer's test value, the right eye will be chosen as the study eye.

All the efficacy analyses will be performed on the study eye only.

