# 12.2. Analysis Populations

Analysis populations are defined below:

- The **Full Analysis Set (FAS)** population consists of all randomised patients who received at least one dose of the study device and had at least one post-baseline sign or symptom assessment of the study eye. This will be the population used for efficacy analyses.
- The **Per-Protocol Set (PPS)** will be a subset of FAS, restricted to the patients who fulfil the protocol in the terms of the eligibility, interventions, and outcome assessment. It will be the analysis population for some sensitivity analyses. The determination of the PPS will be done before unmasking.
- The **Safety population** consists of all patients enrolled who received at least one dose of the study device. It will be the analysis population for safety analyses.

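### Corneal clearing is counted as CFS 0 at a visit with no baseline condition, yet eyes with CFS 0 at baseline are eligible, so an unchanged cornea can count as cleared

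*Protocol*

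**What the plan says.** **Counting rule.** Section 12.5.2 states that "the number and percentage of patients reaching a score of 0 at their CFS will be presented by group at each time point", at weeks 2, 4 and 12, with a 95% confidence interval. Section 10.1 supplies the definition: "A CFS grade of 0 represents complete corneal clearing". Section 12.2 says of the Full Analysis Set (FAS): "This will be the population used for efficacy analyses". None of these sets a condition on the corneal grade at baseline.

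**Endpoint.** Section 5.3.2.1 puts clearing inside a change from baseline: "The change of ocular stainings (corneal fluorescein staining (CFS) and clearing and conjunctival staining) between baseline and D28 and between baseline and D84".

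**Entry.** Inclusion criterion 4 in section 7.1 works on the sum of three areas: "OSS score (sum of nasal and temporal interpalpebral conjunctival and corneal vital staining) ≥4 and ≤9 on a modified Oxford scale". The only criterion on the cornea itself is exclusion 1 in section 7.2, "CFS score ≥4 on a modified Oxford scale", which is an upper limit.

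**Study eye.** Section 12.1.2 adds: "If both eyes are eligible, the eye with the highest baseline CFS score will be chosen". It sets no minimum corneal grade.

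**The concern.** Clearing is a transition: a stained cornea becomes unstained. The analysis section counts a state, grade 0 at the visit, over a population that can include corneas with no staining at the start. Such an eye cannot clear, but if it stays at 0 it is a success at every visit.

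The endpoint section describes a change, and the word *reaching* in section 12.5.2 can be read the same way. The protocol therefore supports more than one numerator and denominator without saying which applies.

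At stake is how the clearing table is interpreted. Under the literal reading both arms' rates are too high as clearing rates, and a true difference is diluted. With about 40 patients per arm, an uneven split of eyes at baseline CFS 0 can also produce or hide a difference unrelated to treatment.

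**Working it through.** **1. Plan figures.** The protocol states no figure for clearing. Its one sample-size figure, for the primary test, reproduces: 2 × (1.960 + 1.282)² × 2.5² / 2² = 32.9, so 33 per arm and 66 in total. Allowing for 15% exclusions, 66 / 0.85 = 77.6, which the planned 80 covers. It does not depend on clearing.

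**2. Can baseline CFS 0 enter?** Section 10.1 gives the grades per area as 0, 0.5, 1, 2, 3, 4 and 5. I listed every temporal, cornea and nasal combination with a sum from 4 to 9 and a corneal grade below 4:

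| Corneal grade | Admissible patterns |
|---|---|
| 0 | 29 |
| 0.5 | 29 |
| 1 | 33 |
| 2 | 35 |
| 3 | 36 |
| Total | 162 |

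Examples with cornea 0 are 2 + 0 + 2 = 4 and 3 + 0 + 3 = 6. The count of 29 in 162 shows that such eyes are possible. It says nothing about how many patients will have them.

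The study-eye rule lowers their number but does not remove them. It has no effect when only one eye qualifies or when both eyes have CFS 0.

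**3. Expected effect of the literal rule.** Let f be the share of study eyes with baseline CFS 0, s the share of those still at 0 at the visit, and c the true clearing rate among eyes that started above 0. The reported rate is f·s + (1 − f)·c. If f and s are equal across arms, the expected difference is (1 − f)(c₁ − c₂).

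The documents give none of f, s or c. The table assumes s = 100%, c₁ = 30%, c₂ = 20% and 40 patients per arm, with standard error √[(a(1 − a) + b(1 − b)) / 40] for reported rates a and b:

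| f | Reported rates | Difference (points) | SE (points) |
|---|---|---|---|
| 0 | 30.0% vs 20.0% | 10.0 | – |
| 5% | 33.5% vs 24.0% | 9.5 | 10.1 |
| 10% | 37.0% vs 28.0% | 9.0 | 10.4 |
| 20% | 44.0% vs 36.0% | 8.0 | 10.9 |

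If only 80% of those eyes stay at 0, f = 10% gives 0.08 + 0.9 × 0.30 = 35% versus 0.08 + 0.9 × 0.20 = 26%. The inflation is smaller and the difference is again 9 points.

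**4. The readings side by side at f = 10%, s = 100%.**
- All grade 0 eyes over the FAS: 37% versus 28%.
- Only eyes that started above 0 in the numerator, all FAS in the denominator: 0.9 × 30% = 27% versus 0.9 × 20% = 18%.
- Only eyes that started above 0 in both: 30% versus 20%.

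The same data give three different clearing rates.

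**5. Chance imbalance.** The standard deviation of the between-arm difference in the baseline CFS 0 share is √[2f(1 − f)/40]: 4.9, 6.7 and 8.9 points at f = 5%, 10% and 20%.

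For illustration, take equal true clearing of 25% and 2 versus 6 of 40 eyes at baseline CFS 0:
- (2 + 38 × 0.25)/40 = 28.75%
- (6 + 34 × 0.25)/40 = 36.25%

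The table would show a 7.5-point gap with no treatment effect.

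**6. Precision after restricting to baseline CFS above 0.** With the same assumed rates, the standard error is √[(0.30 × 0.70 + 0.20 × 0.80)/n]: 9.9 points at n = 38, 10.1 at n = 36 and 10.8 at n = 32 per arm. These are no larger than the values in step 3.

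**The case against.** Several points on the other side have weight.

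- **It can be left to the SAP.** The protocol defers analysis details to a SAP, and the denominator of a descriptive table is such a detail. This limits the point but does not remove it. Sections 10.1 and 12.5.2 already state a rule, and a SAP that follows it literally would carry the problem forward.
- **The wording points to the sensible reading.** *Reaching* and the change-from-baseline heading suggest eyes that started above 0. That is fair for the numerator, but the denominator stays open (step 4).
- **The literal count is a legitimate quantity.** The share of all randomised patients with a clear cornea is a coherent comparison. It is, but it should then not be called clearing or listed as a change.
- **Frequency is unknown and the effect is small.** This stands. Having no corneal dot at all while the conjunctiva alone scores at least 4 may be uncommon in this indication. The expected distortion is 0.5 to 2 points against a standard error of 10 to 11. The 2 versus 6 split is a chosen example: a gap of at least 4 patients in either direction has a probability of about 7% at f = 5% and 19% at f = 10%. Even then, 7.5 points is less than one standard error.
- **The fix is partial.** An eye with one corneal dot (grade 0.5) that loses it still counts as cleared. Eyes at baseline 0 that worsen leave the table. Both are true. The worsening remains visible in the corneal staining analyses of sections 12.5.1 and 12.6, although those analyses do not correct the clearing table.

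**Conclusion.** The concern holds, at low severity. The stated rule has no baseline condition, baseline CFS 0 is eligible, and the endpoint section describes clearing as a change. Followed literally, the rule gives clearing rates that are too high in both arms and a difference multiplied by one minus the share of eyes at baseline CFS 0.

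The size rests on assumptions, because the protocol does not give that share. For shares of 5% to 20% and assumed true rates of 30% versus 20%, the expected loss is 0.5 to 2 points of a 10-point difference. Chance imbalance could matter more in a single trial.

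The effect stays within a descriptive secondary endpoint that has a confidence interval but no test or margin. The primary OSS analysis and the sample size are untouched.

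**What to change.** In section 12.5.2, define clearing as the number and percentage with CFS = 0 at the visit among FAS patients whose study-eye baseline CFS is above 0. Alongside it, tabulate the number with baseline CFS 0 by arm. This brings sections 5.3.2.1, 10.1 and 12.5.2 into line.

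The cost is one line of wording and no new data, since corneal staining is already graded at the Baseline visit. The denominator falls somewhat, to about 36 instead of 40 per arm if 10% start at CFS 0. Under the assumed rates the standard error is then 10.1 points, against 10.4 for the rule as written.

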# 12.6. Analysis of Secondary Endpoints

For FAS population, means for OSS score, CFS, conjunctival fluorescein staining, symptoms of ocular discomfort (VAS), TBUT, Schirmer's test and quality of life (NEI-VFQ) score, and their change from baseline will be summarized by analysis visit. The analysis for FAS population will be conducted by treatment groups.

Summary statistics on the scores of Quality of Life variables will be provided as well as their change from baseline at each visit.

Missing data will not be imputed.

# 12.7. Analysis of Safety and Tolerability Endpoints

All safety and tolerability endpoints analyses will be performed with the Safety population.

#### 12.7.1. Adverse Events

An adverse event is treatment emergent if it occurs or worsens after the first dose of study treatment.

Adverse events will be coded using standard medical terminology. Frequencies and percentages will be given as follows: 1) Overall summary; 2) by system organ class and preferred term, 3) by system organ class, preferred term and maximal severity, 4) by system organ class, preferred term and relationship to study devices and study procedure, respectively, and 5) by system organ class, preferred term, maximal severity, and relationship to study devices and study procedure, respectively.

Separate analyses will be performed for AEs and SAEs, and for ocular and systemic AEs and SAEs, respectively. Ocular AEs will be summarized for the study eye and the fellow eye separately.

## 12.7.2. Other Safety Assessments

Other parameters of safety assessments (e.g. slit lamp examination, BCDVA, and IOP) will be summarised at each time point of measurement for each safety population. They will be summarised/ analysed for the study eye and the fellow eye separately. The analysis for safety population will be conducted by treatment group.

# 12.8. Interim Analysis

Not applicable

# **12.9.** Handling of Missing Values

No imputation for missing data will be performed on primary and secondary endpoint analyses. Unless specified otherwise, descriptive summaries will be based on observed cases.

For medical events including AEs, completely or partially missing onset and resolution dates will be imputed in a conservative fashion to be detailed in the Statistical Analysis Plan (SAP). Same rules will be followed to impute the completely or partially missing start and end dates of non-study devices.

#### 13. DIRECT ACCESS TO SOURCE DATA/DOCUMENTS

# 13.1. Study Monitoring

Before an investigational site can enter a patient into the study, a representative of the Sponsor will either visit the investigational study site or review the feasibility questionnaire to:

- Determine the adequacy of the facilities.
- Discuss with the investigator(s) and other personnel their responsibilities with regard to protocol adherence, and the responsibilities of Santen SAS or its representatives. This will be documented in a Clinical Study Agreement between Santen or its designee and the investigator.

During the study, a monitor from Santen or representative will have regular contacts with the investigational site, for the following:

- Provide information and support to the investigator(s).
- Confirm that facilities remain acceptable.
- Confirm that the investigational team is adhering to the protocol, that data are being accurately recorded in the case report forms, and that investigational device accountability checks are being performed.
- Perform source data verification. This includes a comparison of the data in the case report
  forms with the patient's medical records at the hospital or practice, and other records
  relevant to the study. This will require direct access to all original records for each patient
  (e.g. clinic charts).
- Record and report any protocol deviations not previously sent to Santen.
- Confirm non-serious AEs and SAEs have been properly documented on eCRFs and confirm any safety information requiring expedited reporting to ITEC Services (including SAEs and Pregnancies) have been forwarded to ITEC and those SAEs that met criteria for reporting have been forwarded to Santen, to the EC and to the national Competent Authorities.

The monitor will be available between visits if the investigator(s) or other staff needs information or advice.

# 13.2. Audits and Inspections

Authorised representatives of Santen, a regulatory authority (national or foreign), an Independent Ethics Committee or an Institutional Review Board may visit the site to perform audits or inspections, including source data verification. The purpose of an audit or inspection is to

systematically and independently examine all study-related activities and documents to determine whether these activities were conducted, and data were recorded, analysed, and accurately reported according to the protocol, Good Clinical Practice guidelines of the International Conference on Harmonization, and any applicable regulatory requirements. The investigator should contact Santen immediately if contacted by a regulatory agency about an inspection.

# 13.3. Ethics Committee (EC)

A written favourable opinion of EC (as appropriate) must be obtained before starting the study. Initial EC approval, and all materials approved by the EC for this study including the patient consent form and recruitment materials must be maintained by the Investigator and made available for inspection.

# 14. QUALITY CONTROL AND QUALITY ASSURANCE

To ensure compliance with Good Clinical Practices and all applicable regulatory requirements, Santen may conduct a quality assurance audit. Please see Section 13.2 for more details regarding the audit process.

## 15. ETHICS

## 15.1. Ethics Review

The final study protocol, including the final version of the Informed Consent Form, must be approved or given a favourable opinion in writing by an EC. A copy of the letter indicating EC approval or a favourable opinion must be available at the investigational site before the site can enroll any patient into the study.

Any amendment to the protocol must be reviewed by EC in accordance with local requirements. In addition, the EC must approve all advertising used to recruit patients for the study.

Progress reports and notifications of SAEs will be provided to the EC according to local regulations and guidelines.

# 15.2. Ethical Conduct of the Study

The study will be performed in accordance with ethical principles that have their origin in the Declaration of Helsinki and are consistent with ICH/Good Clinical Practice, ISO 14155:2011 "Clinical investigation of medical devices and applicable regulatory requirements. Please see Appendix D Declaration of Helsinki.

## 15.3. Written Informed Consent

The Principal Investigator(s) at each centre will ensure that the patient is given full and adequate oral and written information about the nature, purpose, possible risk and benefit of the study. Patients must also be notified that they are free to discontinue from the study at any time. The

patient should be given the opportunity to ask questions and allowed time to consider the information provided.

The patient's signed and dated informed consent must be obtained before any protocol-directed procedures are performed.

The Principal Investigator(s) must maintain the original, signed Informed Consent Form. A copy of the signed Informed Consent Form must be given to the patient.

In accordance with Act No 78-17 of January 6, 1978 on Information Technology, Data Files and Civil Liberties, the patient will also be informed in writing of his/her right to access, oppose and rectify data recorded in this study.

## 16. DATA HANDLING AND RECORD KEEPING

# 16.1. Inspection of Records

Santen or Santen's designee will be allowed to conduct site visits to the investigation facilities for the purpose of monitoring any aspect of the study. The Investigator agrees to allow the monitor to inspect the device storage area, study drug stocks, drug accountability records, patient charts and study source documents, and other records relative to study conduct.

## 16.2. Retention of Records

The Principal Investigator must maintain all documentation relating to the study for a period of 2 years after the last marketing application approval, or if not approved 2 years following the discontinuance of the test article for investigation. In addition, ICH E6 Section 4.9.5 states that the study records should be retained until an amount of time specified by applicable regulatory requirements or for a time specified in the Clinical Study Ste Agreement between the investigator and sponsor. If it becomes necessary for Santen or the Regulatory Authority to review any documentation relating to the study, the Investigator must permit access to such records.

